
 • For the secondary analysis of Hgb change from baseline to Week 52, a mixed model repeated measures (MMRM) approach will be used with an unstructured covariance matrix to compare the difference in means between arms. The model will be fitted to Hgb data collected after baseline up to Week 52, excluding values collected during the stabilization period (Randomization date + 1 day to <Week 28). The model will include factors for treatment, time, prognostic randomization stratification factors (as randomized, see Section 10.10.2), baseline Hgb and the baseline Hgb by time and treatment by time interaction terms. Analyses will be done with the MIXED procedure in SAS, using the Kenward-Roger option to estimate denominator degrees of freedom and standard errors. This analysis will be performed using all available Hgb values (on and off-treatment) and separately using evaluable Hgb values only (see Section 10.6.3). In the analysis using all available Hgb values, subjects who withdraw from the study before Week 52 are considered to be missing at random and in the analysis using evaluable Hgb values, subjects who permanently discontinue randomized treatment before Week 52 are assumed to be missing at random. • For the Hgb responder analysis, mean Hgb during the EP will be defined as in the while on-treatment supportive analysis (Section 10.6.3). Responders will be subjects with a mean Hgb during the EP that falls within the Hgb analysis range of 10-11.5 g/dL. A Cochran-Mantel-Haenszel (CMH) chi-squared test, adjusting for treatment and the prognostic randomization stratification factors (as randomized, see Section 10.10.2), will be used to compare the number and % of responders between the treatment groups. • For the analysis of % time in range, the method by Rosendaal [Rosendaal, 1993] will be used to calculate the percentage of time (days) a subject's Hgb is below, within and above the Hgb analysis range of 10 to 11.5 g/dL during the EP (Weeks 28-52) and separately during the MP (Week 28 – end of study) (See Section 10.6.3). A van Elteren test (stratified Wilcoxon rank sum test) will be used to compare the percentage of time in range between treatment arms, adjusting for treatment and the prognostic randomization stratification factors (see Section 10.10.2). This analysis will be performed using evaluable Hgb values only. Hodges-Lehmann

Secondary Efficacy Statistical Analyses: Hgb Variability

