
 For the MMRM analysis of change from baseline in Hgb, the NI margin used in the co-primary analysis of Hgb (-0.75 g/dL) will be used for reference in this comparison, thus generating support for non-inferiority if the lower bound of the two-sided 95% CI is above -0.75 g/dL. For the responder analysis, the one-sided CMH p-value will be compared to 0.025 to assess nominal significance. For the percent time in range analysis, a NI margin of -15% will be used as a reference in this comparison, thus generating support for non-inferiority if the lower limit of the two-sided 95% CI of Hodges-Lehmann estimate is above -0.15. If non-inferiority is established, nominal superiority will be achieved if the one-sided p-value is < 0.025.

Supportive Statistical Analyses
Subgroup Analysis

 Subgroup analyses will be performed for the Hgb change from baseline to Week 52 analysis and the Hgb responder during EP analysis, using the region and current ESA use at randomization subgroups only (described in Section 10.9.1 & Section 10.10), in a method similar to that described for the subgroup analyses of the co-primary and principal secondary analyses. Subgroup analyses will be performed for the percent time in range, using the region subgroups only (described in Section 10.9.1 & Section 10.10), in a method similar to that described for the subgroup analyses of the co-primary and principal secondary analyses.

Time to Rescue

Secondary Efficacy Statistical Analyses: Time to Rescue
Endpoint(s)

 Time to stopping randomized treatment due to meeting rescue criteria
Model Specification

 Analysis of the endpoint above will be performed using an analysis model identical to that described for the co-primary MACE analysis. Analysis will include only those efficacy endpoints occurring within the time period for treatment discontinuation. Calculation of time-to-event or censoring is described in further detail in Section 10.6.3. Time to stopping study medication due to meeting rescue criteria is defined as the time from Randomization until the date on which a subject permanently stops study medication due to meeting criteria for rescue.
Model Results Presentation

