10.6.3. Efficacy

10.6.3.1. Hemoglobin Endpoints

Hemoglobin Values
Central Laboratory and HemoCue Hgb Values

 ● When source of Hgb measurement is not specified: 
 ○ For reporting purposes, central laboratory Hgb values will be used, unless otherwise specified. However, if a central laboratory Hgb value is missing, a corresponding non-missing HemoCue Hgb value will be used. This approach will

Hemoglobin Values

be used for the co-primary Hgb analysis.
 
 Some displays may be created for either central laboratory Hgb values only or HemoCue Hgb values only. The central laboratory summary will be considered the primary summary in this case.
Evaluable Hemoglobin Values

 Evaluable Hgb values are on-treatment Hgb values (see Section 10.4.1) that are not taken within the 8 weeks following a red blood cell transfusion, a whole blood transfusion, or a non-randomized ESA treatment which occurs on or after the randomization date. Red blood cell transfusions, whole blood transfusions and non-randomized ESA treatments occurring on or after the randomization date are identified by comparing the start and stop date of the respective transfusion or ESA concomitant medication record to the randomization date.
Imputed Hemoglobin Values

 For each missing value between baseline to Week 52 (inclusive), 200 imputed values will be generated using the multiple imputation method (see Section 7.1.2). The average of these 200 imputed values will be used as the value for this missing value in the summary tables and figures. For co-primary efficacy Hgb analysis and the corresponding subgroup analyses using all available observed and imputed Hgb values (on and off-treatment), Rubin's rules [Rubin, 1987] will be used to combine results of the imputed datasets using SAS PROC MIANALYZE procedure.
EP Hemoglobin Value for Co-primary Hgb Analysis

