 - Rows outlining scenarios involving combinations of scheduled and unscheduled Hgb values of the same type apply to all Hgb summaries and analysis.

Scheduled Central Lab Hgb Value	Unscheduled Central Lab Hgb Value	Scheduled HemoCue Hgb Value	Unscheduled HemoCue Hgb Value	Value to Use	Type/Label
x				Scheduled central lab Hgb value	Scheduled visit
	x			Unscheduled central lab Hgb value	Unscheduled
		x		Scheduled HemoCue Hgb value	Scheduled visit
		multiple ¹		Average of scheduled HemoCue Hgb values	Scheduled visit
			x	Unscheduled HemoCue Hgb value	Unscheduled
	multiple			Average of unscheduled central lab Hgb values	Unscheduled
			multiple	Average of unscheduled HemoCue Hgb values	Unscheduled
x	x			Average of central lab Hgb values	Scheduled visit
x		x		Scheduled central lab Hgb value	Scheduled visit
x			x	Scheduled central lab Hgb value	Scheduled visit
	x	x		Unscheduled central lab Hgb value	Unscheduled
	x		x	Unscheduled central lab Hgb value	Unscheduled
		x	x	Average of HemoCue Hgb values	Scheduled visit

1: The dose adjustment algorithm will require sites to obtain two HemoCue Hgb values at some visits.

Time In Range

Time in Range During the EP

- Number of days that a subject's evaluable Hgb is within the analysis range of 10-11.5 g/dL inclusive during the EP (See Section 10.6.1), including any unscheduled evaluable Hgb values that were taken during this time period.
- Use of unscheduled Hgb values follows the scenarios for unscheduled and multiple Hgb values.
- Linear interpolation is used to estimate Hgb between visits, accounting for any intermittent missing values [Rosendaal, 1993].

Percent Time in Range During the EP

- Time in Range During the EP / [Earlier of (Date of the last evaluable Hgb value, Week 52 visit date) – Later of (Date of the first evaluable Hgb value that between Week 16 and Week 52

Time In Range

inclusive, Week 28 visit date)]
 
 Note: Percent time in/below/above range during the EP is only defined for subjects with a Treatment Stop Date that is on or after their Week 28 visit date, and have at least two evaluable Hgb values on different days, where at least one evaluable Hgb value is contained within the EP and another evaluable Hgb value occurs within the range of the Week 16 visit through 4 weeks following the Week 52 visit, inclusive.
Time in Range During the MP

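### Percent time in range is interpolated across the 8-week windows whose Hgb values the SAP itself excludes, so those days are scored without usable data and the error can go either way

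*SAP*

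**What the plan says.** Section 10.6.3.1 defines evaluable Hgb values as on-treatment values "that are not taken within the 8 weeks following a red blood cell transfusion, a whole blood transfusion, or a non-randomized ESA treatment" on or after randomization. Time in range is then the "Number of days that a subject's evaluable Hgb is within the analysis range of 10-11.5 g/dL inclusive during the EP", and for days between measurements "Linear interpolation is used to estimate Hgb between visits, accounting for any intermittent missing values". The same rule applies to the MP. No maximum interpolation gap is given for either period.

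The EP denominator begins "Time in Range During the EP / [Earlier of (Date of the last evaluable Hgb value, Week 52 visit date" and subtracts the later of the first evaluable value from Week 16 on and the Week 28 visit. The MP denominator is built the same way up to the End of Study date. Neither subtracts the excluded windows. A subject qualifies if, among other conditions, they "have at least two evaluable Hgb values on different days".

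Section 8.1.1.2 says of the test: "This analysis will be performed using evaluable Hgb values only". For interpretation, "a NI margin of -15% will be used as a reference in this comparison", followed by nominal superiority at one-sided 0.025. No all-values or gap-limited sensitivity analysis is listed for this endpoint. Section 8.1.2.2 applies the same interpolation method to the percentage of time with Hgb at or above 12 g/dL.

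**The concern.** The two rules work against each other. The evaluable definition sets post-event values aside because they no longer reflect randomized treatment alone. Interpolation then refills those same weeks with a straight line and counts them as fully as observed weeks. The values are not intermittently missing in the ordinary sense: they were measured and deliberately discarded.

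This also sits badly with the supportive analysis in Section 7.1.2.5. That analysis uses the same evaluable values, targets the effect in the absence of transfusion and non-randomized ESA, and states that nothing is imputed. At stake is a secondary endpoint tested for non-inferiority and then nominal superiority, for both EP and MP, plus the exploratory time at or above 12 g/dL.

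**Working it through.** The SAP states no figure for this rule, so there is none to reproduce. The check applies the rule to visit times and to invented subjects.

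**Inputs from the SAP**
- EP: 7 scheduled values, Weeks 28 to 52, every 4 weeks, so 6 × 28 = 168 days (Sections 7.1.2.5 and 10.2.1.1).
- After Week 52: visits every 12 weeks (Section 10.2.1.1).
- Exclusion window: 8 weeks = 56 days. Range: 10 to 11.5 g/dL. Margin: 15 percentage points.

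**Length of the bridge**
- Let the last visit before the event be on day v and the event on day t, with v ≤ t < v + 28.
- Visits v + 28 and v + 56 are both no later than t + 56, so both are dropped. Visit v + 84 is later than t + 56, so it is kept.
- The bridge is 84 days: 84/168 = 50% of the EP. The window alone is 56/168 = 33%.
- After Week 52, one dropped 12-weekly value leaves 2 × 12 = 24 weeks.
- Unscheduled evaluable values can shorten these bridges.

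**Subject A (assumed values): in range on both sides.** Hgb is 10.6 at five visits and 9.0 at days 56 and 84, both dropped.
- All measured values: the line falls from 10.6 to 9.0 and crosses 10 after 0.6/1.6 × 28 = 10.5 days; the return adds another 10.5 days in range. Days out of range: 84 − 21 = 63. Time in range: 105/168 = 62.5%.
- SAP rule: 168/168 = 100%. Difference: +37.5 points.

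**Subject C (assumed values): low value captured before the event.** Hgb is 10.6 on day 0, 8.5 on day 28, 10.5 on days 56 and 84 (dropped), then 10.6.
- All measured values: 0.6/2.1 × 28 = 8 days, plus 28 − 1.5/2.0 × 28 = 7 days, plus 112 days = 127/168 = 75.6%.
- SAP rule: 8 days, plus 84 − 1.5/2.1 × 84 = 24 days, plus 56 days = 88/168 = 52.4%. Difference: −23.2 points.

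The all-values figures are not the truth, since the dropped values are affected by the other treatment. They show how far the score depends on the line.

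**Arm level, mean scale, assumed rates.** Shift = error per affected subject × between-arm difference in the proportion affected.
- 25 points × 5% = 1.25 points; 50 points × 10% = 5 points.
- A 15-point shift would need a difference of 15/50 = 30% to 15/25 = 60% of subjects.
- The planned estimate is Hodges-Lehmann, so these mean shifts are only indicative.

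**Effect of removing the bridged days (28 to 112)**
- Subject A: 84/84 = 100%. With those days counted as not in range: 84/168 = 50%.
- Subject C: (8 + 56)/84 = 64/84 = 76.2%. With those days counted as not in range: 64/168 = 38.1%.

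**The case against.** A reader might infer that the rule credits a patient's worst weeks as in range, favours the arm with more transfusions or rescue, and so weakens the non-inferiority test. The documents do not support that.
- **Direction.** Only values after the event are dropped. A low value before it, scheduled or not, stays evaluable and anchors the line, as in Subject C. The SAP does not say that Hgb is low in the excluded weeks; after a transfusion it may be higher.
- **Rescue.** Sections 2.2 and 8.1.1.2 define the rescue endpoint by permanent stop of randomized treatment. Under Section 10.4.1.1, Hgb more than one day after the treatment stop date is post-treatment and so not evaluable. The denominator ends at the last evaluable value, so that time is truncated, not bridged.
- **Size.** The SAP gives no event rates, and similar rates in the two arms would largely cancel.
- **Consequence.** The endpoint carries no multiplicity adjustment, its margin is a reference, and superiority is nominal. The co-primary analysis keeps all values regardless of transfusion or ESA. Transfusions and non-randomized ESA use are tabulated by arm.
- **Remedy.** Removing the days does not change the score of a subject who is in range on both sides.

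All of this stands, and it limits the point. It does not answer the internal conflict: excluding the values is a declared choice, but scoring the excluded weeks from a line does not follow from it.

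**Conclusion.** The point holds as a derivation defect of limited consequence. For a subject who remains on randomized treatment and later has an evaluable value, up to half of the EP, and about 24 weeks of the MP for one dropped value, can be scored from a line drawn over deliberately excluded time. An individual score can move by tens of points in either direction, as the assumed subjects show. The arm-level effect cannot be determined from the SAP. Under the assumed 5 to 10 percentage-point imbalance in affected subjects it is about 1 to 5 points on the mean scale, likely small against the 15-point margin. Rescue with permanent treatment stop and the co-primary Hgb analysis are not affected. The change is worth making because it is cheap and removes invented days from a tested endpoint.

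**What to change.** In Section 10.6.3.1, for both EP and MP, state that there is no interpolation between two evaluable values when a transfusion or non-randomized ESA exclusion window lies between them. Remove all days between those two values from numerator and denominator. Defining the removal from one evaluable value to the next also settles the days between the last pre-event value and the event, which would otherwise have no rule. Apply the same rule to the percentage of time with Hgb at or above 12 g/dL in Section 8.1.2.2.

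Because removal alone still scores a subject who is in range on both sides as 100%, add to Section 8.1.1.2 a sensitivity analysis of percent time in range that keeps those days in the denominator and counts them as not in range.

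The cost is SAP wording and a small program change. Some denominators become shorter, and a few subjects may be left without a defined value.

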10.6.3.2. Iron Endpoints

Iron Endpoints																													
Iron Medications																													

 • During the study, subjects may be receiving iron in multiple routes, including: 
 ○ IV iron ○ Oral iron ○ Other iron (including intramuscular, subcutaneous, and hemodialysis/dialysate) • Note: The iron route categories above will be determined using the route on the Prior/Concomitant Medication – Iron Therapy record. In addition, ferric citrate records recorded on the Prior/Concomitant Medication – Metabolic Bone Disease Therapy eCRF form will also be summarized as oral iron use. 																													
Baseline Iron Use																													

 • The number and percentage of subjects in the following iron use categories at baseline will be summarized: 
 ○ IV iron use only ○ Oral iron use only ○ Other iron use only ○ IV and oral iron use only ○ IV and other iron use only ○ Oral and other iron use only ○ IV, oral, and other iron use ○ No iron use • When determining baseline iron use, the gap factors mentioned below will be applied to the end date for each iron record, and a period of 16 weeks before the Randomization date until the day before the Randomization date will be used as the baseline period. 																													

  
 Frequency of Iron Concomitant Medication Record (from eCRF)	Gap Factor	
   
 2 times per week	2.5 days	
 
 3 times per week	1.33 days	
 
 4 times per week	0.75 day	
 
 5 times per week	0.4 day	
 
 BID	0 days	
 
 Once daily	0 days	
 
 One time dose	n/a	
 
 Every 12 Hours	0 days	
 
 Every 2 weeks	13 days	
 
 Every 4 weeks	27 days	
 
 Once a month	29 days	
 
 Once a week	6 days	
 
 TID	0 days	
  
	Frequency of Iron Concomitant Medication Record (from eCRF)	Gap Factor	2 times per week	2.5 days	3 times per week	1.33 days	4 times per week	0.75 day	5 times per week	0.4 day	BID	0 days	Once daily	0 days	One time dose	n/a	Every 12 Hours	0 days	Every 2 weeks	13 days	Every 4 weeks	27 days	Once a month	29 days	Once a week	6 days	TID	0 days	
Frequency of Iron Concomitant Medication Record (from eCRF)	Gap Factor																												
2 times per week	2.5 days																												
3 times per week	1.33 days																												
4 times per week	0.75 day																												
5 times per week	0.4 day																												
BID	0 days																												
Once daily	0 days																												
One time dose	n/a																												
Every 12 Hours	0 days																												
Every 2 weeks	13 days																												
Every 4 weeks	27 days																												
Once a month	29 days																												
Once a week	6 days																												
TID	0 days																												

Iron Endpoints

 After the addition of the gap factor, IV iron therapy concomitant medication records that occur or are ongoing during the period from the Randomization date – 16 weeks to the Randomization date will be selected and used to create the categories of iron use listed above.
Iron Use by Quarter

 The number and percentage of subjects in the following iron use categories defined by route will be summarized by quarters listed below: 
 IV iron use only Oral iron use only Other iron use only IV and oral iron use only IV and other iron use only Oral and other iron use only IV, oral, and other iron use No iron use When determining iron use by quarter, the gap factors mentioned above will also be applied to the end date for each iron record. Iron use will be summarized by quarters, where quarters will be defined using study visits as follows: 
 Baseline For summaries of on & off treatment IV iron: 
 Quarter 1 = [Randomization date – Week 12) For summaries of on-treatment IV iron: 
 Quarter 1 = [Treatment start date + 1 – Week 12) Quarter 2 = [Week 12 – Week 24) Quarter 3 = [Week 24 – Week 36) Etc. To determine the planned start date and end date of quarters, the visit end date (from the SV domain) will be used. If there is not a corresponding visit, or if the subject is missing that visit, the planned visit date (Randomization date + 7*x) will be used, where x is the scheduled week (e.g., Week 24, x = 24). A subject's quarterly iron use will end at the earliest of the following: 
 For summaries of on & off treatment iron use: death date, study completion/withdrawal date, and the planned quarter end date. For summaries of on-treatment iron use: death date, study completion/withdrawal date, treatment stop date + 1, and the planned quarter end date. Although baseline iron use is defined based on a period of 16 weeks, it will also be included in summaries of iron use by quarter.
TIBC

 TIBC will be calculated automatically by the central laboratory using: 
 $TIBC = UIBC + \text{total iron}$
TSAT

 TSAT will be calculated automatically by the central laboratory using: 
 $TSAT = 100 * (\text{Serum Iron} / TIBC)$

Iron Endpoints
Average Quarterly TSAT and Ferritin

 The average TSAT and Ferritin values will be summarized by quarters, where quarters will be defined as they are for Iron Use by Quarter, with the following exception: 
 Baseline average quarterly ferritin and TSAT will take the average of all available records before or on randomization ferritin and TSAT values. 
Note: any unscheduled values falling within these quarters will be used in the calculation of the quarterly average value.

Meeting Iron Management Criteria

Iron therapy will be administered if at any visit:
 
 Ferritin \leq 100 ng/mL and/or TSAT \leq 20% 
All iron must be stopped if at any visit:
 
 Ferritin $>$ 800 ng/mL and TSAT $>$20%, or TSAT $>$ 40% 
Subjects meeting iron management criteria requiring starting and stopping of iron administration on the same day:
 
 Ferritin \leq100 ng/mL and TSAT $>$ 40%

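### The baseline iron-use rule selects only IV records for categories meant to cover every route, and the by-quarter display sets a 16-week baseline beside 12-week quarters

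*SAP*

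**What the plan says.** All of this stands in SAP Section 10.6.3.2 (Iron Endpoints), unless noted.

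- **Routes in scope.** Iron may be IV, oral or other. Ferric citrate recorded on the metabolic bone disease form "will also be summarized as oral iron use". Eight categories follow: three single routes, three pairs, all three routes, and none. The covariate table in Section 10.10.1 lists the same eight for the demographic and baseline summary.
- **Baseline window.** "a period of 16 weeks before the Randomization date until the day before the Randomization date will be used as the baseline period". Within it, "the gap factors mentioned below will be applied to the end date for each iron record", with no restriction by route.
- **Baseline selection rule.** After the gap factors are added, "IV iron therapy concomitant medication records that occur or are ongoing during the period from the Randomization date" minus 16 weeks up to the randomization date itself "will be selected and used to create the categories of iron use listed above".
- **Quarters.** The later periods are 12 weeks long, for example "Quarter 2 = [Week 12 – Week 24" (end week excluded). For the on-and-off-treatment summary, Quarter 1 starts on the randomization date, inclusive. Both Quarter 1 definitions are labelled as IV iron, although the eight route categories are repeated for the quarters and "the gap factors mentioned above will also be applied to the end date for each iron record".
- **Baseline in the quarterly display.** "Although baseline iron use is defined based on a period of 16 weeks, it will also be included in summaries" by quarter. No rescaling or footnote is specified.

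**The concern.** The selection sentence is the instruction that a programmer would code, and it cannot produce the categories it is meant to fill. The result feeds the baseline-characteristics table as well as the quarterly display, so the share of subjects entering the trial on iron would be misstated in both.

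The window lengths raise a second, independent problem. The proportion with any use grows with the length of the window unless use is continuous. A 16-week baseline column beside 12-week quarters can therefore suggest a change in iron use after randomization when there was none.

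**Working it through.** The plan states no iron-use rates, so there is no figure to reproduce. The route and date points are settled by comparing the text; the size of the window effect rests on assumed rates, shown as a range.

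**1. What an IV-only selection can fill.** If only IV records are selected, each subject either has one or has none.

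| True use at baseline | Category assigned |
|---|---|
| IV only, or IV with any other route | IV only |
| Oral only, other only, oral and other | None |
| None | None |

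Two of the eight categories can be filled, and 8 − 2 = 6 are always empty.

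**2. End date.** One sentence stops the baseline on the day before randomization; the selection rule runs to the randomization date. Quarter 1 (on and off treatment) includes that date. Under the selection rule, iron given that day counts in both periods. The on-treatment Quarter 1 starts one day after treatment start, so its lower limit does not create this overlap.

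**3. Window length, all routes selected.** The ratio of windows is 16/12 = 1.33. For intermittent iron at a constant rate,

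P(any use in 16 weeks) = 1 − (1 − p)^(16/12), where p is the proportion with any use in 12 weeks.

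| Assumed p | 16-week reading | Apparent fall (points) | Fall relative to baseline |
|---|---|---|---|
| 10% | 13.1% | 3.1 | 3.1/13.1 = 24% |
| 20% | 25.7% | 5.7 | 5.7/25.7 = 22% |
| 30% | 37.9% | 7.9 | 7.9/37.9 = 21% |

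Gap factors lengthen both windows. With about four weeks of carry-over the comparison is roughly 20 against 16 effective weeks, so the exponent is 20/16. The same three rates then give apparent falls of 2.3, 4.3 and 6.0 points. Subjects on iron throughout show no fall.

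**4. Direction when the IV-only rule is applied literally and the quarters count all routes.** Assume 10% IV use per 12 weeks and, independently, 20% continuous oral use.

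- Baseline (IV only, 16 weeks): 13.1%.
- Quarter 1 (all routes, 12 weeks): 1 − 0.90 × 0.80 = 28.0%.
- Apparent change: 28.0 − 13.1 = +14.9 points, a rise.

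Across oral use of 10–40% and 12-week IV use of 5–20%, every combination run gave a rise, from 2.3 to 36.4 points. With 5% oral use the sign depends on IV use: +1.4 points at 10% IV, −1.7 at 20% IV.

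**5. After correction.** With all routes selected but 16 weeks kept, the apparent fall over those IV rates and oral use of 0–40% is 1.0 to 5.7 points. With a 12-week baseline as well, it is zero under the model.

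**The case against.** The strongest reply is that 'IV' is an evident drafting slip. The surrounding text applies the gap factors to every iron record, counts ferric citrate as oral iron and lists eight categories, so a careful programmer would probably select all routes. That makes the miscount less likely, but the wrong word sits in the operative rule and the Quarter 1 labels repeat it, so the text still needs correcting.

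The 16-week window is disclosed, applies identically to both arms, and feeds only descriptive output. Section 10.10.1 does not use baseline iron use for subgroup analysis. Iron use by quarter is not among the exploratory iron endpoints in Section 2.2 or the iron rows of Table 6. All of this stands and keeps the point minor. Disclosing the length does not make the columns comparable, however.

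A reader might infer that the two defects together manufacture a fall in iron use, and hence an appearance of iron sparing. They do not: the long window raises the baseline and the IV-only rule lowers it, usually by more once oral use exceeds a few percent. A reader might also take this display as the plan's only view of iron need. Section 8.1.2.2 also plans ferritin, TSAT, hepcidin, total iron and TIBC by visit, quarterly ferritin and TSAT, and counts of subjects meeting iron-management criteria.

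**Conclusion.** Two wording faults and one comparability fault hold.

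- The selection rule contradicts the categories it serves. Taken literally, it codes oral-only and other-only users as non-users at baseline, in the baseline-characteristics table too. This needs no assumption about rates.
- The two baseline end dates differ by a day, and under one of them the randomization date can be counted twice. The effect is small.
- With all routes selected, the 16-week baseline overstates any use of intermittent iron relative to a 12-week quarter: 3.1, 5.7 or 7.9 points at 12-week use of 10%, 20% or 30%. This assumes a constant rate and no carry-over; gap factors reduce it, and continuous users contribute nothing.

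The documents do not support a claim of bias between arms, since the same window applies to both. Nor do they support a fall in every category: the categories are mutually exclusive, so a longer window can move a subject from a single-route category into a combination. The point is minor but cheap to correct.

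**What to change.** In SAP Section 10.6.3.2:

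1. In the baseline selection sentence, replace the restriction to IV iron therapy with all iron therapy records, and name the ferric citrate records from the metabolic bone disease form explicitly.
2. Remove 'IV' from both Quarter 1 definitions; otherwise Quarter 1 would conflict with the corrected baseline.
3. End the baseline window on the day before randomization in both sentences.
4. In the by-quarter display, compute baseline use over the 12 weeks ending the day before randomization. Keep the 16-week figure, labelled as such, in the baseline-characteristics table.

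The cost is SAP wording and one changed date limit, because those 12 weeks lie inside the period already used. The downside is two baseline iron figures, each needing a footnote.
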